7.2.3. Liver-related Laboratory Evaluations

The summary will be provided by 3 subgroups of subjects according to their baseline ALT/AST level in the Randomized/OL Phase:

- Normal
- Elevated (> 1 to $< 5 \times$ upper limit of normal [ULN])
- Elevated ($\geq 5 \times$ ULN)

Liver-related abnormalities after initial study drug dosing will be examined and summarized using the number and percentage of subjects who were reported to have the following laboratory test values for postbaseline measurements:

For subjects with normal baseline ALT/AST:

- Subjects meeting criteria for close observation
 - $ALT/AST > 3 \times ULN$
- Subjects meeting criteria for holding study drug
 - $ALT/AST > 8 \times ULN$
 - $ALT/AST > 5 \times ULN$ for 2 weeks
 - $ALT/AST > 3 \times ULN$ and total bilirubin $> 2 \times ULN$ (or direct bilirubin $2 \times$ baseline in subjects with Gilbert's syndrome)
 - $ALT/AST > 3 \times ULN$ and $INR > 1.5$ (if not on anticoagulation)

For subjects with baseline ALT/AST between 1 and $5 \times ULN$

- Subjects meeting criteria for close observation
 - $ALT/AST > 2 \times$ Baseline or > 300 U/L
- Subjects meeting criteria for holding study drug
 - $ALT/AST > 8 \times$ Baseline or > 500 U/L
 - $ALT/AST > 3 \times$ Baseline or > 300 U/L, and total bilirubin $> 2 \times ULN$ (or direct bilirubin $2 \times$ Baseline in subjects with Gilbert's syndrome)
 - $ALT/AST > 3 \times$ Baseline and $INR > 1.5$ (if not on anticoagulation)

For subjects with baseline $ALT/AST \geq 5 \times ULN$

- Subjects meeting criteria for close observation
 - $ALT/AST > 2 \times$ Baseline
- Subjects meeting criteria for holding study drug
 - $ALT/AST > 500$ U/L

The above summary will include data from all postbaseline visits up to 30 days after the last dose of study drug for subjects who permanently discontinued study drug (and before OL Study Day 1 for abnormalities in the Randomized Phase) in the reporting phase, or the last available date in the database snapshot for subjects who were still on treatment at the time of an interim analysis. The denominator is the number of subjects in the (OL) Safety Analysis Set who have nonmissing

postbaseline values of all relevant tests at the same postbaseline visit date in the summarizing group. A listing of subjects meeting any of the criteria above will be provided.

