Potential risks of this study include those related to the fact that SEL is a new chemical entity with a long term safety profile that has yet to be established. In nonclinical studies, profuse diarrhea was the dose limiting toxicity in cynomolgus monkeys. In Phase 2 clinical studies in AH, PAH, DKD, and NASH, a greater proportion of subjects treated with SEL (66 of 565 [11.7%]) had an adverse event of diarrhea compared to placebo- or SIM-treated subjects (13 of 184 [7.1%]). However, diarrhea was generally mild and self-limited. Across the development program, drug discontinuation rates were low and not attributable to a single AE with increased frequency. In Phase 2 clinical studies in subjects with NASH, AH, DKD, or PAH, rates of elevations in liver tests (ALT or AST  $> 3 \times$  upper limit of normal [ULN] and  $> 2 \times$  baseline for the NASH studies; ALT or AST  $> 5 \times$  baseline for the AH study; ALT or AST  $> 3 \times$  ULN for the DKD and PAH studies) were observed in SEL-treated subjects (17 of 564 [3.0%]) and placebo-treated subjects (4 of 182 [2.2%]). In many of these cases, an alternative and/or confounding etiology was identified including alcohol use, intercurrent illness, or concomitant treatment with medications known to cause hepatotoxicity. However, in some cases, a plausible alternate etiology was not identified. To mitigate the potential risk of liver injury in the planned Phase 3 NASH program, subjects will be monitored closely; defined rules for close observation and drug cessation due to elevated liver tests have been specified in Section 7.5; and all potential cases of drug-induced liver injury (DILI) will be adjudicated by an independent DILI adjudication committee. In addition, embryofetal toxicity was observed in nonclinical studies; therefore to prevent potential fetal exposure, adherence to effective methods of contraception will be required during the Phase 3 program.

Additional risks to study subjects include those attributable to study participation in general, including risks associated with frequent clinic visits and laboratory blood draws, and the associated pain and discomfort of phlebotomy. Strategies to mitigate these risks include close monitoring of lab values as well as AEs. Parameters for discontinuation of the study drugs due to AEs and non-hepatic laboratory abnormalities are also defined and will be closely followed.

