### 4.2. Inclusion Criteria

Subjects must meet all of the following inclusion criteria to be eligible for participation in this study.

- 1) Willing and able to give informed consent prior to any study specific procedures being performed
- 2) Liver biopsy consistent with NASH (defined as the presence of at least grade 1 steatosis, hepatocellular ballooning, and lobular inflammation according to the NAFLD Activity Score [NAS]) and bridging (F3 fibrosis) according to the NASH CRN classification, in the opinion of the central reader
  - a) A historical liver biopsy within 6 months of the Screening visit may be accepted as the Screening biopsy if the sample is deemed acceptable for interpretation by the central reader
  - b) If the subject is deemed ineligible for this study, the liver biopsy, if performed according to protocol specifications and is within 12 months of the Screening visit, may be used to determine eligibility for study GS-US-384-1944
- 3) Subject has the following laboratory parameters at the Screening visit, as determined by the central laboratory:
  - a)  $ALT \leq 8 \times ULN$
  - b)  $CL_{cr} \geq 30 \text{ mL/min}$ , as calculated by the Cockcroft-Gault equation
  - c)  $HbA1c \leq 9.5\%$  (or serum fructosamine  $\leq 381 \mu\text{mol}$  if HbA1c is unable to be resultd)
  - d) Total bilirubin  $\leq 1.3 \times ULN$  (unless an alternate etiology such as Gilbert's syndrome or hemolytic anemia is present)
  - e)  $INR \leq 1.4$ , unless due to therapeutic anti-coagulation
  - f) Platelet count  $\geq 100,000/\mu\text{L}$
- 4) Body Mass Index (BMI)  $\geq 18 \text{ kg/m}^2$  at Screening

- 5) Males and non-pregnant, non-lactating females between 18-70 years of age; inclusive based on the date of the Screening visit
- 6) Females of childbearing potential (as defined in [Appendix 3](#)) must have a negative pregnancy test at Screening and Day 1
- 7) Male subjects and female subjects of childbearing potential who engage in heterosexual intercourse must agree to use protocol specified method(s) of contraception as described in [Appendix 3](#)

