**Close observation includes:**

- Repeating liver biochemistries (ALT, AST, ALP, GGT, total bilirubin, INR) and obtaining a creatine phosphokinase (CPK) level within 48-72 hours of results
- Obtaining a more detailed history of symptoms and prior or concurrent disease
- Obtaining a history of concomitant drug use (including nonprescription medications and herbal and dietary supplement preparations), alcohol use, recreational drug use, and special diets
- Obtaining a history of exposure to environmental chemical agents
- Ruling out other causes of liver disease as needed (obtain viral hepatitis panel, imaging for evaluation of biliary tract disease, etc. if required in the opinion of the primary investigator)
- Continue to monitor liver biochemistries at least twice weekly. Frequency can decrease to once a week or less if abnormalities stabilize or study drug has been discontinued and the subject is asymptomatic

During close observation, study drug can be continued, if desired, at the discretion of the Gilead Medical Monitor and the Principal Investigator.

If on-treatment elevations of ALT and/or AST exceed the values shown in Figure 7-2, are confirmed on repeat testing within 48-72 hours of results, and no alternative cause is immediately apparent, the subject must be placed into close observation and study drug must be withheld.

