**Figure 7-2. On-Treatment ALT/AST Monitoring Requiring Study Drug Withholding**

Subjects who develop signs or symptoms of liver toxicity (such as right upper quadrant discomfort, fever, nausea, vomiting, jaundice, rash, or eosinophilia > 5%) which are suspected by the principal investigator to be drug-related, must have study drug withheld and be placed into close observation.

If study drug is withheld, it may be reintroduced with approval from the Medical Monitor if another etiology of elevated liver tests is identified. Study drug must be discontinued if close monitoring is not possible or if total bilirubin, ALT or AST elevation recurs following re-challenge with study drug. Subjects who discontinue study drug due to suspected hepatotoxicity must be followed until symptoms subside, any abnormal laboratory values have resolved or returned to baseline levels, until there is a satisfactory explanation for the changes observed, or for 3 months after drug discontinuation, whichever is longer.

Treatment-emergent toxicities will be noted by the Investigator and brought to the attention of the Medical Monitor. Whether or not considered treatment-related, all subjects experiencing AEs must be monitored periodically until symptoms subside, any abnormal laboratory values have resolved or returned to baseline levels or they are considered irreversible, or until there is a satisfactory explanation for the changes observed.

Other than in the case of the liver enzymes noted above, Grade 3 or 4 clinically significant laboratory AEs should be confirmed by repeat testing as soon as practical to do so, and preferably within 3 calendar days of receipt of the original test results.

Any questions regarding toxicity management should be directed to the Medical Monitor.

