7.2.4. Drug-Induced Liver Injury (DILI)

Due to the challenge of recognizing and diagnosing DILI in subjects with pre-existing hepatic dysfunction, a DILI Adjudication Committee will review potential cases of DILI identified based on laboratory parameters listed in Section 7.2.3. Proportion of subjects with DILI events determined by the Adjudication Committee, including confirmed DILI events (or worsening of hepatic function attributable to study drug could not be excluded) and insufficient data, will be summarized by treatment group for the Randomized and OL Phase. Multiple events will be counted only once per subject for each phase. All adjudicated DILI events will be listed for All Randomized Analysis set.

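### SAP 7.2.3 has no combined ALT/AST-plus-bilirubin (or INR) criterion for baseline ALT/AST of 5 x ULN or more, so on a plain reading some bilirubin rises are neither listed nor identified for DILI review by the SAP's laboratory rules

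*SAP*

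**What the plan says.** SAP 7.2.3 splits subjects into three strata by baseline ALT/AST (normal, 1 to 5 x ULN, and 5 x ULN or more). Each stratum has criteria for close observation and for holding study drug.

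The two lower strata pair an ALT/AST threshold with total bilirubin above 2 x ULN, and another with INR above 1.5. In the 1 to 5 x ULN stratum the bilirubin line contains "Baseline or > 300 U/L, and total bilirubin", so there an absolute limit of 300 U/L is enough on the enzyme side. The top stratum has two lines only: above 2 x Baseline for close observation, and "ALT/AST > 500$ U/L" for holding drug (the dollar sign is left over from text conversion).

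Two sentences make the list matter. SAP 7.2.3 ends: "A listing of subjects meeting any of the criteria above will be provided". SAP 7.2.4 then says that "a DILI Adjudication Committee will review potential cases of DILI identified based on laboratory parameters listed in Section 7.2.3". Protocol 1.5 gives the intention: "all potential cases of drug-induced liver injury (DILI) will be adjudicated by an independent DILI adjudication committee".

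**The concern.** The stratum can be populated: Protocol 4.2 admits ALT up to 8 x ULN and sets no AST limit. It is also where injury is hardest to separate from underlying disease, which is the reason SAP 7.2.4 gives for having the committee. Yet it is the only stratum where a bilirubin or INR rise adds nothing to the criteria.

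In the Randomized Phase, bilirubin above 2 x ULN is normally a new finding, because Screening bilirubin must be at most 1.3 x ULN "unless an alternate etiology such as Gilbert's syndrome or hemolytic anemia is present". Likewise, Screening INR must be at most 1.4 unless the subject is anticoagulated. Protocol 1.5 reports ALT/AST elevations in 17 of 564 subjects on selonsertib (3.0%) and 4 of 182 on placebo (2.2%) in Phase 2, some without a plausible other cause, and offers adjudication as part of the mitigation. At stake is how completely possible cases are tabulated and identified. No efficacy result, alpha or power figure is affected.

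**Working it through.** **1. The criteria side by side** (SAP 7.2.3; B = baseline ALT/AST; entries are ALT/AST thresholds)

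| Stratum | Close observation | Hold, enzyme alone | Hold, with bilirubin > 2 x ULN | Hold, with INR > 1.5 |
|---|---|---|---|---|
| Normal | > 3 x ULN | > 8 x ULN, or > 5 x ULN for 2 weeks | > 3 x ULN | > 3 x ULN |
| 1 to 5 x ULN | > 2B or > 300 U/L | > 8B or > 500 U/L | > 3B or > 300 U/L | > 3B |
| 5 x ULN or more | > 2B | > 500 U/L | none | none |

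**2. The resulting windows.** In the top stratum with bilirubin above 2 x ULN:

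- No criterion is met when ALT/AST ≤ min(2B, 500). I report this from 3 x ULN upward, the enzyme level that the normal stratum pairs with bilirubin.
- Close observation only is met when 2B < ALT/AST ≤ 500. This is empty once B ≥ 250 U/L.

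The documents give no ULN, so a range is assumed (all values in U/L):

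| Assumed ULN | No criterion, B = 5 x ULN | Close observation only, B = 5 x ULN | No criterion, B = 8 x ULN |
|---|---|---|---|
| 30 | 90 to 300 | 300 to 500 | 90 to 480 |
| 35 | 105 to 350 | 350 to 500 | 105 to 500 |
| 40 | 120 to 400 | 400 to 500 | 120 to 500 |
| 45 | 135 to 450 | 450 to 500 | 135 to 500 |
| 50 | 150 to 500 | none | 150 to 500 |

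At B = 8 x ULN the close-observation-only window is 480 to 500 for ULN 30 and empty otherwise.

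As a check, the printed rules were coded and run over baselines of 5 to 8 x ULN, ULN 30 to 55, and several bilirubin and INR values. Of 206,400 combinations with ALT/AST ≤ 2B and ≤ 500 U/L and bilirubin above 2 x ULN, none met a criterion.

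**3. Two neighbouring subjects** (ULN 40 assumed, bilirubin 3 x ULN)

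- Baseline 205: 2B = 410. ALT of 205 or 320 meets nothing; ALT of 450 meets close observation only.
- Baseline 195: ALT of 320 exceeds 300, so both close observation and hold are met. ALT of 290 is below 300 and below 2B = 390, so nothing is met. This stratum therefore has its own smaller window, 120 to 300 U/L.

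**4. Which omission does what.** In the 1 to 5 x ULN stratum, anyone above 3B or 300 U/L is also above 2B or 300 U/L. The bilirubin line there moves subjects into the hold count but adds nobody to the listing. Relative to that stratum, the top stratum's listing gap comes from the missing 300 U/L limit, and the missing bilirubin line affects the hold count.

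**5. What other outputs show** (SAP 7.2, 7.2.2.3 and Appendix 2). From an abnormal baseline, ALT/AST ≤ 2B is at most Grade 1. Bilirubin reaches Grade 3 above 3 x ULN from a normal baseline, or above 3 x baseline from an abnormal one: 3 x 1.3 = 3.9 x ULN for a baseline at the entry limit. Below that, the rise is missing from the Grade 3 or 4 listing. It does appear in the graded summary and as a flag in the general laboratory listing, but test by test, not as a combination with ALT/AST.

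**The case against.** **The operative rules are in the protocol.** Protocol 3.3.3 sends possible cases to the committee by reference to Section 7.5, and drug is withheld there "If on-treatment elevations of ALT and/or AST exceed the values shown in Figure 7-2". Figures 7-1 and 7-2 are not visible. They may contain a bilirubin rule for this stratum, which would leave only a reporting mismatch. If they do not, the SAP may simply mirror them. This stands. A reader might infer that the SAP contradicts the protocol, or that subjects with rising bilirubin may stay on drug. The documents support neither inference.

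**SAP 7.2.4 says parameters, not criteria.** Bilirubin and INR are among the tests named in 7.2.3, so the sentence could mean the analytes. That is possible, but the SAP would then give no threshold for identifying a case. The criteria reading is the workable one, though it remains an assumption.

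**ALT and AST might be classed separately.** SAP 7.2.3 does not say. Take ULN 40, ALT rising from 205 to 320, AST from 160 to 310, and bilirubin 3 x ULN. Both enzymes are at or below 2B (410 and 320) and 500. If AST is classed separately, its 310 exceeds 300 and meets close observation and, with bilirubin, hold. This stands as a limit.

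**Much of the window has no enzyme rise.** At ULN 40 it starts at 120 U/L although baseline is at least 200. A bilirubin rise alone in advanced fibrosis need not be drug injury. That is true, but classifying such cases is the committee's task.

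**The data are not lost.** Graded summaries, laboratory flags, the medical monitor and the DMC all remain. Subjects with signs such as jaundice "which are suspected by the principal investigator to be drug-related, must have study drug withheld and be placed into close observation". That trigger depends on the investigator suspecting the drug, and SAP 7.2.4 names none of these routes as its source of cases. The cover is partial.

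**Conclusion.** The omission in the SAP text is clear: the top stratum has no bilirubin or INR combination, and the other two have both. The consequence is conditional. If each subject falls in one stratum and 7.2.4 relies on the 7.2.3 criteria, a subject with bilirubin above 2 x ULN and ALT/AST ≤ min(2B, 500 U/L) is absent from the 7.2.3 count and listing, and the SAP's laboratory rules do not identify that subject for DILI review. Above 2B but at or below 500 U/L, the subject is listed and referable but counted under close observation only. Cases above 500 U/L meet the hold criterion.

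A reader might go further and conclude that such cases escape adjudication altogether. The documents do not show that, because the protocol route cannot be seen and clinical routes exist. The number of subjects is not given and is probably small. This is a minor point, certain as to the SAP wording and less so as to actual referral.

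**What to change.** Add two reporting lines to SAP 7.2.3, identical in all three strata:

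- ALT/AST above 3 x ULN together with total bilirubin above 2 x ULN (in Gilbert's syndrome, direct bilirubin at 2 x Baseline instead).
- ALT/AST above 3 x ULN together with INR above 1.5, if not on anticoagulation.

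Use them for the count, the listing and DILI referral only. Do not label them drug-holding criteria, since Figure 7-2 may not contain them. In the same edit, state whether ALT and AST are classed separately and that 7.2.4 relies on the criteria.

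The lines should cover every stratum. Added to the top stratum alone, at ULN 40 and the same raised bilirubin, they would flag a baseline of 205 falling to 125 but miss a baseline of 195 rising to 290. Covering all strata also closes the 120 to 300 U/L window at baseline 195. Borrowing the 300 U/L limit instead would still miss a stable ALT of 205.

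The cost is a few lines of text. Chemistry and coagulation are drawn at every scheduled clinic visit, the existing INR criteria already need anticoagulant use, and the committee exists. If the SAP is already final, SAP section 1 provides for recording the change in the study report. The downside is a few extra reviews. Every subject in the top stratum starts above 3 x ULN, so a bilirubin or INR rise alone can meet a line, and in the Open-Label Phase so can disease progression. The committee can classify such cases as DILI excluded (Protocol 3.3.3).

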7.2.4. Drug-Induced Liver Injury (DILI)

Due to the challenge of recognizing and diagnosing DILI in subjects with pre-existing hepatic dysfunction, a DILI Adjudication Committee will review potential cases of DILI identified based on laboratory parameters listed in Section 7.2.3. Proportion of subjects with DILI events determined by the Adjudication Committee, including confirmed DILI events (or worsening of hepatic function attributable to study drug could not be excluded) and insufficient data, will be summarized by treatment group for the Randomized and OL Phase. Multiple events will be counted only once per subject for each phase. All adjudicated DILI events will be listed for All Randomized Analysis set.

7.3. Body Weight and Vital Signs

Descriptive statistics will be provided by treatment group for body weight, waist circumference, BMI and vital signs (systolic and diastolic blood pressure [mmHg], pulse [bpm], respiratory rate [breath/min] and temperature [°C]) in the Randomized/OL Phase as follows:

- Baseline value
- Value at each postbaseline visit
- Change from baseline at each postbaseline visit
- Percent change from baseline at each postbaseline visit (only for body weight)

A baseline value in the Randomized/OL Phase will be defined as the last available value collected on or prior to the date/time of first dose of study drug in the corresponding treatment phase. Change from baseline to a postbaseline visit will be defined as the postbaseline value minus the baseline value. Vital signs measured at unscheduled visits will be included for the baseline value selection. **CCI**

In the case of multiple values in an analysis window, data will be selected for analysis as described in Section 3.8.3. No formal statistical testing is planned.

A by-subject listing of vital signs will be provided by subject ID number and visit in chronological order. A by-subject listing of body weight, height, BMI and waist circumference will be provided.

7.4. Prior and Concomitant Medications

Medications collected at Screening and during the study will be coded using the current version of the World Health Organization (WHO) Drug dictionary.

7.4.1. Prior Medications

Prior medications are defined as any medication taken before a subject took the first study drug in the Randomized Phase.

Prior medications will be summarized by preferred name using the number and percentage of subjects for each treatment group and overall. A subject reporting the same medication more than once will be counted only once when calculating the number and percentage of subjects who received that medication. The summary will be ordered by preferred name in order of descending overall frequency. For drugs with the same frequency, sorting will be done alphabetically.

For the purposes of analysis, any medication with a start date prior to the first dosing date of study drug will be included in the prior medication summary regardless of when the stop date is. If a partial start date is entered the medication will be considered prior unless the month and year (if day is missing) or year (if day and month are missing) of the start date are after the first dosing date. Medications with a completely missing start date will be included in the prior medication summary, unless otherwise specified.

Summaries will be based on the Safety Analysis Set. No formal statistical testing is planned.

7.4.2. Concomitant Medications

Concomitant medications are defined as medications taken while a subject took study drug. Use of concomitant medications will be summarized by preferred name using the number and percentage of subjects for each treatment group in the Randomized/OL Phase. A subject reporting the same medication more than once will be counted only once when calculating the number and percentage of subjects who received that medication. The summary will be ordered by preferred name in descending frequency in the (OL) SEL 18 mg group for the Randomized/OL Phase. For drugs with the same frequency, sorting will be done alphabetically.

For the purposes of analysis, any medication with a start date prior to or on the first dosing date of study drug and continued to take after the first dosing date, or started after the first dosing date but prior to or on the last dosing date of study drug will be considered concomitant medications. Medications started and stopped on the same day as the first dosing date or the last dosing date of study drug will also be considered concomitant. Medications with a stop date prior to the date of first dosing date of study drug or a start date after the last dosing date of study drug will be excluded from the concomitant medication summary. If a partial stop date is entered, any medication with the month and year (if day is missing) or year (if day and month are missing) prior to the date of first study drug administration will be excluded from the concomitant medication summary. If a partial start date is entered, any medication with the month and year (if day is missing) or year (if day and month are missing) after the study drug stop date will be excluded from the concomitant medication summary. Medications with completely missing start and stop dates will be included in the concomitant medication summary, unless otherwise specified. Summaries will be based on the (OL) Safety Analysis Set. No formal statistical testing is planned.

All prior and concomitant medications (other than per-protocol study drugs) will be provided in a by-subject listing sorted by subject ID number and administration date in chronological order.

